5.2 Exclusion criteria

Subjects meeting any of the following criteria are not eligible for inclusion in this study.

1. Subjects with unresectable or metastatic disease. All patients should have brain imaging (either MRI brain or CT brain with contrast) prior to enrollment to exclude brain metastasis.
2. History of severe hypersensitivity reactions to monoclonal antibodies, which in the opinion of the investigator may pose an increased risk of serious infusion reaction.
3. Presence or history of a malignant disease that has been diagnosed and/or required therapy within the past 3 years. Exceptions to this exclusion include the following: completely resected basal cell and squamous cell skin cancers, and completely resected carcinoma in situ of any type.
4. Subjects who received prior systemic therapy (including chemotherapy, other anti-cancer therapies and any other antibody or drug specifically targeting T-cell co-stimulation or immune checkpoint pathways) in the past 3 years before screening.
5. Active autoimmune disease that has required systemic treatment in the past 2 years prior to randomization (i.e. with use of disease modifying agents, corticosteroids or immunosuppressive drugs). Control of the disorder with replacement therapy (e.g., thyroxine, insulin, or physiologic corticosteroid replacement therapy for adrenal or pituitary insufficiency, etc) is permitted.
6. Uncontrolled diabetes as defined per the investigator.
7. History of (non-infectious) pneumonitis that required steroids or current pneumonitis.

8. Clinically significant, uncontrolled heart disease and/or recent cardiac event (within 6 months), such as:
 - a. Unstable angina or myocardial infarction within 6 months prior to screening
 - b. History of documented congestive heart failure (CHF) (New York Heart Association functional classification III-IV)
 - c. Uncontrolled hypertension defined by a Systolic Blood Pressure (SBP) \geq 160 mm Hg and/or Diastolic Blood Pressure (DBP) \geq 100 mm Hg, with or without anti-hypertensive medication. Initiation or adjustment of antihypertensive medication(s) is allowed prior to randomization
 - d. Ventricular arrhythmias
 - e. Supraventricular and nodal arrhythmias not controlled with medication
 - f. Other cardiac arrhythmia not controlled with medication
9. Major surgery (e.g., intra-thoracic, intra-abdominal or intra-pelvic) within 4 weeks prior to randomization or who have not recovered from side effects of such procedure. Video-assisted thoracic surgery (VATS) and mediastinoscopy will not be counted as major surgery and patients can be enrolled in the study \geq 1 week after the procedure.
10. Subject with suspected or proven immunocompromised state or infections, including:
 - Evidence of active or latent tuberculosis (TB) as determined by locally approved screening methods. If presence of TB (active or latent) is established then treatment for TB must have been completed according to locally approved country guidelines prior to screening for the study.
 - Chronic or active hepatitis B or C
 - Known history of testing positive for Human Immunodeficiency Virus (HIV) infections. For countries where HIV status is mandatory: testing positive for HIV during screening using a local test.
 - Any other medical condition (such as active infection, treated or untreated), which in the opinion of the investigator places the patient at an unacceptable risk for participation in immunomodulatory therapy. Subjects with localized condition unlikely to lead to a systemic infection e.g. chronic nail fungal infection are eligible.
 - Allogeneic bone marrow or solid organ transplant
 - Subject receiving any biologic drugs targeting the immune system (for example, TNF α blockers, anakinra, rituximab, abatacept, or tocilizumab).
 - Current treatment with any immune modulating agent in doses with systemic effects e.g.:
 - Current systemic glucocorticoid therapy except for daily glucocorticoid-replacement for conditions such as adrenal or pituitary insufficiency and topical, inhaled or local steroid use in doses that are not considered to cause systemic effects are permitted
 - Prednisone $>$ 20 mg (or equivalent) daily for $>$ 14 days;
 - Prednisone $>$ 5 mg and \leq 20 mg (or equivalent) daily for $>$ 30 days;
 - Equivalent dose of methotrexate $>$ 15 mg weekly.
11. Live vaccination within 3 months prior to randomization.

12. Subjects who have received an investigational drug or device within 5 half-lives prior to randomization or those who are expected to participate in any other investigational drug or device during the conduct of the study.
13. Pregnant or breast-feeding (lactating) women, or women who plan to become pregnant or breast-feed during the study, where pregnancy is defined as the state of a female after conception and until the termination of gestation, confirmed by a positive human chorionic gonadotropin (hCG) laboratory test.
14. Women of child-bearing potential, defined as all women physiologically capable of becoming pregnant, unless they are using highly effective contraception during the study and for 4 months after stopping study treatment.
 - Total abstinence (when this is in line with the preferred and usual lifestyle of the subject. Periodic abstinence (e.g., calendar, ovulation, symptothermal, postovulation methods) and withdrawal are not acceptable methods of contraception)
 - Female sterilization (have had surgical bilateral oophorectomy with or without hysterectomy), total hysterectomy or bilateral tubal ligation at least 6 weeks before taking study treatment. In case of oophorectomy alone, only when the reproductive status of the woman has been confirmed by follow up hormone level assessment
 - Male sterilization (at least 6 months prior to screening). For female patients on the study, the vasectomized male partner should be the sole partner for that patient.
 - Use of oral (estrogen and progesterone), injected or implanted combined hormonal methods of contraception or placement of an intrauterine device (IUD) or intrauterine system (IUS), or other forms of hormonal contraception that have comparable efficacy (failure rate <1%), for example hormone vaginal ring or transdermal hormone contraception.

In case of use of oral contraception, women should have been stabilized on the same pill for a minimum of 3 months before taking study treatment.

Women are considered post-menopausal and not of child bearing potential if they have had 12 months of natural (spontaneous) amenorrhea with an appropriate clinical profile (e.g. age appropriate, history of vasomotor symptoms) or have had surgical bilateral oophorectomy (with or without hysterectomy) or bilateral tubal ligation at least 6 weeks ago. In the case of oophorectomy alone, only when the reproductive status of the woman has been confirmed by follow up hormone level assessment is she considered not of child-bearing potential.

15. Subject has any other concurrent severe and/or uncontrolled medical condition that would, in the investigator's judgment, cause unacceptable safety risks, contraindicate subject participation in the clinical study, or compromise compliance with the protocol (e.g. chronic pancreatitis, uncontrolled diabetes mellitus).

6 Treatment

6.1 Study treatment

In this study, the “study treatment” refers to both canakinumab and pembrolizumab study drugs administered either as monotherapy or in combination of study drugs: canakinumab plus pembrolizumab. The term “investigational drug” refers to the Novartis study drug, canakinumab (ACZ885).

6.1.1 Investigational and control drugs

Table 6-1 Investigational and control drug

Study treatment	Pharmaceutical Dosage Form and route of administration	Strength	Dose	Frequency and/or regimen
Canakinumab (ACZ885)	Solution for s.c. injection in prefilled syringe	150 mg/1 mL AND 50 mg/0.5 mL	200 mg	Q3W
Pembrolizumab ^a	Concentrate for solution for i.v. infusion in vial Lyophilized powder for solution for i.v. infusion in vial	100 mg/4 mL (25 mg/mL) 50 mg	200 mg	Q3W

^a Either concentrate solution or lyophilized powder formulations of pembrolizumab can be used if approved by local country regulations.

For preparation and dispensation please refer to [Section 6.7](#)

6.1.2 Additional study treatments

No other treatment beyond investigational drug and control drug are included in this trial.

6.1.3 Treatment arms/group

Subjects will be randomized at cycle 1 Day 1 visit to one of the following 3 treatment arms/groups (canakinumab alone or canakinumab in combination with pembrolizumab or pembrolizumab alone) in a ratio of 2:2:1.

For preparation and dispensation please refer to [Section 6.7](#).

6.1.4 Guidelines for continuation of treatment

Guidelines for management of toxicities and dose modification instructions please refer to [Section 6.5](#).

Continuation of treatment beyond the 2 cycles prior and after the surgery is not permitted.

6.1.5 Treatment duration

Subjects will receive a maximum of two cycles of treatment (Q3 weeks). After the second study drug administration (Cycle 2), study treatment will be completed and subject will undergo the surgical procedure (4 to ~6 weeks after the first study drug administration). Study treatment can discontinue earlier in case of disease progression radiologically documented by investigator assessment, unacceptable toxicity that precludes further treatment, at the discretion of the investigator, subject withdrawal of consent, pregnancy, lost to follow-up, or death. No crossover treatment between the arms is allowed.

6.2 Other treatment(s)

6.2.1 Concomitant therapy

In general, the use of any concomitant medications/non-drug therapies deemed necessary for the care of the subject (e.g. Granulocyte Colony-Stimulating Factor [G-CSF], anti-emetics, anti-diarrhea) is permitted except when specifically prohibited ([Section 6.2.2](#)). For pembrolizumab, please refer to the locally approved label.

The investigator should instruct the subject to notify the study site about any new medications and/or non-drug therapies/procedures he/she takes after signing the informed consent. All medications including herbal/natural medications and significant non-drug therapies/procedures (including surgeries, physical therapy and blood transfusions) taken within 28 days of screening and administered after the subject has signed informed consent must be listed on the appropriate electronic case report form (eCRF) pages.

Subjects taking concomitant medication chronically should be maintained on the same dose and dose schedule throughout the study period, as medically feasible. The days of PK blood sampling should be representative of the other study days with regard to the use of the chronically administered concomitant medications. However, if a concomitant medication is used intermittently during the study, this medication should be avoided on the days of PK sampling, if medically feasible.

Each concomitant drug must be individually assessed against all exclusion criteria/prohibited medications. If in doubt, the investigator should contact the Novartis medical monitor before randomizing a subject or allowing a new medication to be started. If the subject is already randomized, contact Novartis to determine if the subject should continue participation in the study.

6.2.1.1 Permitted concomitant therapy requiring caution and/or action

6.2.1.1.1 Permitted concomitant medications

Medications required to treat AEs, manage cancer symptoms, concurrent diseases and supportive care agents, such as pain medications, anti-emetics and anti-diarrheal are allowed. Potential drug interactions between study drugs and concomitant medications should always be taken into consideration *Note: For Drug-Drug interaction (DDI) potential, please refer to [Section 1.2.3](#) .*

Antibodies that modulate cytokines, which may regulate cytochrome P450 (CYP450) enzymes, may cause DDI with small molecule drugs because of the potential to alter CYP-mediated metabolism ([Harvey and Morgan 2014](#)). Anti-cytokine antibodies such as canakinumab that target and neutralize these proinflammatory cytokines or their receptors are capable of restoration of CYP450 enzymes to normal levels ([Ashino et al 2007](#)). This is clinically relevant for CYP450 substrates with a narrow therapeutic index. Caution should be exercised when administering these agents (see [Table 6-2](#)) concomitantly with canakinumab.

Given the potential DDI via cytokine modulation by canakinumab, subjects who are on warfarin or warfarin-like treatment with narrow therapeutic index, should have their international normalized ratio (INR) measured locally and warfarin or warfarin-like treatment dose adjusted accordingly within one month from starting study treatment.

6.2.2 Prohibited medication

6.2.2.1 Prohibited concomitant medications for canakinumab

Use of any treatments below are NOT allowed after the start of study treatment due to potential increase in immunosuppressant related concomitant conditions. They are prohibited for the duration of the study and for at least 130 days after discontinuation of canakinumab.

Note: steroids are allowed at any dose/duration when necessary to treat immune-related adverse events (irAE). Investigators should closely monitor subjects for risk of infections.

- Any anti retro-virals and/or any biologic drugs targeting the immune system (e.g., TNF α blockers, anakinra, rituximab, abatacept, tocilizumab)
- Treatment with any immune modulating agent in doses with systemic effects e.g.:
 - Prednisone > 20 mg (or equivalent) oral or intravenous daily for > 14 days;
 - Prednisone > 5 mg and \leq 20 mg (or equivalent) daily for > 30 days;
 - Equivalent dose of methotrexate > 15 mg weekly
- Topical, inhaled or local steroid use in doses that are not considered to cause systemic effects are permitted
- Live vaccines within 90 days of study treatment and after initiation of study treatment. Subjects must be discontinued from study treatment if administered any live vaccine during the course of the study. *Note: Inactivated vaccines are allowed.*

The following treatments are NOT allowed after the start of study treatment and until surgery.

- Any additional investigational drugs, devices, chemotherapy, or any antineoplastic therapies that may be active against cancer.

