6.5.1 Dose modifications

For subjects who do not tolerate the protocol-specified dosing schedule the following principles must be followed:

- For both canakinumab and pembrolizumab dose reductions are not permitted.

- Increase in the canakinumab dosing interval to Q6W is not applicable due to the short duration of the study.
- Canakinumab dose interruption for a maximum of 1 week is allowed as per [Table 6-2](#).
- Pembrolizumab will follow locally approved labels (if pembrolizumab is not yet approved in your country, refer to [Section 16.1](#)) and local clinical practice.

All dose changes in any study drugs must be recorded on the appropriate eCRF page.

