General instructions: 
 1. Corticosteroids taper should be initiated upon AE improving to Grade 1 or less and continue to taper over at least 4 weeks. 2. For situations where pembrolizumab has been withheld, pembrolizumab can be resumed after AE has been reduced to Grade 1 or 0 and corticosteroid has been tapered. 3. For severe and life-threatening irAEs, IV corticosteroid should be initiated first followed by oral steroid. Other immunosuppressive treatment should be initiated if irAEs cannot be controlled by corticosteroids. 				
Immune related AEs	Toxicity grade or conditions (CTCAEv4.0)	Action taken to pembrolizumab	irAE management with corticosteroid and/or other therapies	Monitor and follow-up
AST /ALT elevation or Increased bilirubin	Grade 2	Withhold	
 • Administer corticosteroids (initial dose of 0.5-1 mg/kg prednisone or equivalent) followed by taper 	
 • Monitor with liver function tests (consider weekly or more frequently until liver enzyme value returned to baseline or is stable).
	Grade 3 or 4	Permanently discontinue	
 • Administer corticosteroids (initial dose of 1-2 mg/kg prednisone or equivalent) followed by taper 	
Type 1 diabetes mellitus (T1DM) or Hyperglycemia	Newly onset T1DM or Grade 3 or 4 hyperglycemia associated with evidence of beta-cell failure	Withhold	
 • Initiate insulin replacement therapy for participants with T1DM • Administer anti-hyperglycemic in participants with hyperglycemia 	
 • Monitor participants for hyperglycemia or other signs and symptoms of diabetes.
Hypophysitis	Grade 2	Withhold	
 • Administer corticosteroids and initiate hormonal replacements as clinically indicated. 	
 • Monitor for signs and symptoms of hypophysitis (including
	Grade 3 or 4	Withhold or permanently discontinue ¹		

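### Section 6.2.2.1 bars the non-steroid immunosuppression that Table 16-1 says should be started for steroid-refractory irAEs, a direct conflict at combination-arm sites using Appendix 1; whether the ban covers the pembrolizumab-alone arm is unclear

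*Protocol*

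**What the plan says.** **The prohibition (Protocol 6.2.2.1).** The section is headed as applying to canakinumab. From the start of study treatment it bars "any biologic drugs targeting the immune system", giving TNF-alpha blockers, anakinra, rituximab, abatacept and tocilizumab as examples. It also bars a second class: "Treatment with any immune modulating agent in doses with systemic effects e.g". On duration: "They are prohibited for the duration of the study and for at least 130 days after discontinuation of canakinumab". The only irAE exemption is a note that "steroids are allowed at any dose/duration when necessary to treat immune-related adverse events (irAE").

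**The opposing instruction (Protocol 16.1, Table 16-1, general instruction 3).** For severe and life-threatening irAEs, corticosteroids come first. Then: "Other immunosuppressive treatment should be initiated if irAEs cannot be controlled by corticosteroids".

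**Where Table 16-1 applies (Protocol 6.5.1).** "Pembrolizumab will follow locally approved labels (if pembrolizumab is not yet approved in your country, refer to" Section 16.1), together with local clinical practice.

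**General permission (Protocol 6.2.1 and 6.2.1.1.1).** Section 6.2.1.1.1 allows these: "Medications required to treat AEs, manage cancer symptoms, concurrent diseases and supportive care agents". Section 6.2.1 says that concomitant medication needed for the subject's care "is permitted except when specifically prohibited", and points to 6.2.2 for the prohibitions. For pembrolizumab it refers to the local label.

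**The concern.** Table 16-1 asks for a second step when steroids fail. Section 6.2.2.1 exempts the first step and not the second. A site that follows both texts cannot comply with both, and the clash falls on severe or life-threatening events. Stopping study drug does not clear it, because the prohibition continues after canakinumab is discontinued.

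The second issue is scope. The heading of 6.2.2.1 and its 130-day clock name canakinumab only, while its start trigger is study treatment in general. Sites could read the rule differently for the pembrolizumab-alone arm. At stake are subject safety and the consistent recording of protocol deviations across arms.

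**Working it through.** **1. The one figure in the rule.** Section 3 gives the 130-day follow-up as five half-lives, and Section 4.2.1 gives 26 days for canakinumab: 5 × 26 = 130 days. The figure reproduces, and the point does not depend on it. The documents give no separate half-life for pembrolizumab. With the second dose on Day 22 (Table 6-4), a clock dated from that dose runs to at least Day 22 + 130 = Day 152.

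**2. Do the two texts overlap?** Table 16-1 names no agent. Section 6.2.2.1 names classes broad enough to take in immune-targeting biologics and any immune modulator at systemic doses. An agent given to suppress a severe irAE systemically falls within those classes unless it is a steroid.

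**3. Does another clause settle it?**
- Sections 6.2.1 and 6.2.1.1.1: the permission to treat adverse events yields to specific prohibitions, so on the text the ban prevails.
- Section 6.5.1.1: the rule to follow the more conservative course concerns dose modification, not concomitant drugs.
- Section 6.2.1: doubt about a new medication goes to the sponsor's medical monitor. That is a route to an answer; it does not supply one.
- Section 14.1: immediate action for a subject's safety is expected even where it departs from the protocol. The action is then still a deviation.

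None of these removes the conflict.

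**4. At which sites?** Section 6.5.1 refers to Section 16.1 only where pembrolizumab is not yet approved. Combination-arm sites there hold both instructions. At other sites the protocol supplies the prohibition, and the local label, which is not in the documents, decides whether anything opposes it.

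**5. Which arms?**
- *Towards canakinumab only:* the heading, the 130-day clock, the lack of a matching pembrolizumab subsection in 6.2.2, and the label referral in 6.2.1.
- *Towards all arms:* the ban starts with study treatment, which Section 6.1 defines to include pembrolizumab alone, and it runs for the duration of the study. Follow-up extends to 130 days after the end-of-treatment visit in every arm (Sections 3, 9.1.1 and 9.2).

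On the second reading the study-duration limb gives an end point for pembrolizumab alone, but the canakinumab clock has nothing to start from. The text does not choose between the readings.

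**6. How many subjects?** Planned allocation, 110 in 2:2:1:
- combination: 110 × 2/5 = 44
- pembrolizumab alone: 110 × 1/5 = 22

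The conflict can reach at most 44 planned subjects if the ban covers canakinumab arms only, or 44 + 22 = 66 if it covers all arms. The number at Appendix 1 sites is not given. The documents state no steroid-refractory rate. Taking 1% to 5% purely as an assumption:
- combination: 44 × 0.01 = 0.44 to 44 × 0.05 = 2.2
- pembrolizumab alone: 22 × 0.01 = 0.22 to 22 × 0.05 = 1.1

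**7. Statistical reach.** The primary estimand lists two intercurrent events: new antineoplastic therapy before surgery and discontinuation of study treatment before surgery (Protocol 12.4.2, SAP 1.2.1). Rescue immunosuppression is neither. In SAP Table 2-3 the only protocol deviation that removes a subject from an analysis set is missing written consent. The response rule and its operating characteristics do not change.

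**The case against.** The strongest reply is that most sites may never meet the conflict. Section 1.1.2 says pembrolizumab is approved in many countries, and at such sites Section 6.5.1 makes the local label the guide. This stands. A reader might infer that every combination-arm site has contradictory orders; the documents do not support that.

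Table 16-1 also uses should, not must, so rescue is recommended and not strictly required. This stands too, but a recommendation that the same protocol prohibits still needs reconciling.

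Sections 6.2.1 and 14.1 give investigators a way to act, and Section 10.1.1 asks that all adverse events be treated appropriately. These soften the consequence. They work by consultation or by accepting a deviation, not by making the instructions agree.

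A reader might further infer that the combination and pembrolizumab-alone arms have different rescue rules, and that irAE duration or time to surgery would be biased as a result. The text shows an ambiguity of scope and no settled difference. The plan contains no analysis of irAE duration or time to surgery: adverse events are summarised as counts and percentages, and surgical feasibility is a binary rate. A ban limited to canakinumab arms could also be deliberate, given its stated rationale of added immunosuppression.

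Finally, the SAP records that recruitment was halted on 1 February 2022, so the practical benefit is confined to subjects still within the restricted window.

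**Conclusion.** The concern holds within limits. Section 6.2.2.1 and Table 16-1, general instruction 3, give opposing directions on non-steroid immunosuppression for irAEs that corticosteroids do not control. The conflict is explicit for combination-arm sites that use Section 16.1. Elsewhere it depends on labels that cannot be checked here. Whether the ban covers the pembrolizumab-alone arm, and until when, is unclear.

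The size is small in numbers: up to about 2 of 44 planned combination subjects and about 1 of 22 on pembrolizumab alone, under an assumed refractory rate of at most 5% and before allowing for sites that follow a local label. The point matters for subject safety and clean deviation records. It does not touch the primary analysis of major pathological response, the sample size or the error rates.

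**What to change.** The sponsor's medical team should reconcile Section 6.2.2.1 with Table 16-1, general instruction 3, so that one consistent instruction covers irAEs not controlled by corticosteroids. The heading, start trigger and end point of 6.2.2.1 should also be made consistent about which arms the section covers. Which clinical rule and which window are right is for the medical team; this review proposes neither.

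The cost is a sentence or two in 6.2.2.1, Table 16-1 or both, and a letter to sites. There is no sample-size or analysis change. The deviation and concomitant-therapy listings already planned in SAP 2.3 and 2.4.2 should help to identify any subject affected.
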